### **13.1.3. Primary Effectiveness Endpoint 2: Pre-MR Scan vs. 1 Month Post-MR Scan RV Pacing Threshold at 0.5 ms**

Subjects that have an increase in average pacing thresholds  $\leq 0.5$ V (at 0.5 ms) from pre-MR Scan to MRI Visit + 1 Month follow-up will be considered a success, otherwise, it is a primary effectiveness endpoint 2 event.

The performance goal of this endpoint for the ENABLE MRI study was 87%. There is no hypothesis testing in the MR ICD study, and it can be considered reasonable if up to 2 failed cases of primary effectiveness endpoint 2 occur.

The data set for the primary effectiveness endpoint 2 will only include subjects who undergo the study-required MR scan and complete all the sequences, and will not include subjects that meet any of the following exclusions:

- Has a medically necessary scan between implant and the MRI + 1 Month Visit
- Fails to meet labeled MRI Conditions of Use
- Experiences a lead-related complication between MRI Visit and the MRI + 1 Month Visit

The time window for MRI + 1 Month visit is  $30\pm7$  days post MR scan, so it will capture events within at least 23 days post scan. In this small sample size study, missing data will be excluded.

#### **13.1.4. Primary RV Effectiveness Endpoint 3: Pre-MR scan vs. 1 Month Post-MR Scan RV Sensed Amplitude**

Subjects will be considered a success if the average sensed amplitude at the MRI + 1 Month Visit remains  $\geq 5.0$  mV and above 50% of the pre-MR scan value, otherwise, it is a primary effectiveness endpoint 3 event.

The performance goal of this endpoint for the ENABLE MRI study was 85%. There is no hypothesis testing in the MR ICD study, and it can be considered reasonable if up to 2 failed cases of primary effectiveness endpoint 3 occur.

The data set for the primary effectiveness endpoint 3 will only include subjects who undergo the study-required MR scan and complete all the sequences, and will not include subjects that meet any of the following exclusions:

- Has a medically necessary scan between implant and the MRI + 1 Month Visit
- Fails to meet labeled MRI Conditions of Use
- Experiences a lead-related complication between MRI Visit and the MRI + 1 Month Visit
- Average RV sensed amplitude  $<5$ mV pre-MR scan

The time window for MRI + 1 Month visit is  $30\pm7$  days post MR scan, so it will capture events within at least 23 days post scan. In this small sample size study, missing data will be excluded.

### **13.1.5. Primary Effectiveness Endpoint 4: Pre MR Scan- vs. 1 Month Post-MR Scan LV Pacing Threshold at 0.5 ms**

Subjects that have an increase in average pacing thresholds  $\leq 1.0V$  (at 0.5 ms) from pre-MR Scan to MRI Visit + 1 Month follow-up will be considered a success, otherwise, it is a primary effectiveness endpoint 4 event.

The performance goal of this endpoint for the ENABLE MRI study was 87%. There is no hypothesis testing in the MR ICD study, and it can be considered reasonable if up to 2 failed cases of primary effectiveness endpoint 4 occur.

The data set for the primary effectiveness endpoint 4 will only include subjects who undergo the study-required MR scan and complete all the sequences, and will not include subjects that meet any of the following exclusions:

- Has a medically necessary scan between implant and the MRI + 1 Month Visit
- Fails to meet labeled MRI Conditions of Use
- Experiences a lead-related complication between MRI Visit and the MRI + 1 Month Visit

The time window for MRI + 1 Month visit is  $30\pm 7$  days post MR scan, so it will capture events within at least 23 days post scan. In this small sample size study, missing data will be excluded.

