Primary Statistical Hypothesis	This study is a single-arm, small sample clinical study without any hypothesis testing. It can be considered reasonable if up to 2 failed cases of primary safety endpoint event occur. It can be considered reasonable if up to 2 failed cases of endpoint event occur in each of the five primary effectiveness endpoints.
Statistical Test Method	Descriptive statistics will be conducted for the endpoint events.
Sample Size Parameters	This study is a single-arm, small sample clinical study without any hypothesis testing. Twenty subjects (10 with ICD and 10 with CRT-D) will be enrolled. It is assumed that the attrition should not be more than 2 cases in each group, so that at least 8 subjects shall be included in the final analysis for each group.

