#### **12.5.1.3. Manual Left Ventricular Threshold Test**

If the subject does not have an active implanted LV lead, then skip to the next section. If multiple manual LV threshold tests are performed, then record the manual LV threshold test that matches the final programmed LV lead configuration following these steps:

1. In the Left Ventricular Threshold Test screen set the Test Type to Amplitude
2. Mode, Lower Rate Limit, Amplitude and Paced AV delay shall be set per physician or HCP discretion
3. Pulse Width shall be set to 0.5 ms
4. Cycles per Step shall be set to a minimum of 3
5. Start the annotated real-time ECG from the PRM, then start the manual LV threshold test
  - 1) A count of 2 non-capture beats at a given voltage level is required to declare loss of capture (LOC)
  - 2) If the subject experiences discomfort during the threshold test due to extracardiac stimulation, then stop the test and perform the manual threshold test per physician discretion.
6. When LOC is determined, stop the threshold test. Stop the PRM real-time ECG a

minimum of 2 seconds after LOC is determined.

7. Label the PRM ECG with the subject ID#, date, Visit name, and “Manual LV threshold test”.
8. The threshold for the manual LV threshold test is defined as one voltage level above the level where the 2 non-captured beats are observed. Record the threshold in the EDC system.
9. If the threshold saved on the PRM does not match the threshold, as defined in step 8, then update the LV Pace Threshold in the programmer.

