## **13. Statistical Considerations**

### **13.1. Primary Endpoints**

#### **13.1.1. Primary Safety Endpoint: MR Scan-Related ImageReady System Complication Free Rate**

The primary safety endpoint of the MR ICD study will be assessed for all subjects who undergo any portion of the study-required MR scan sequences. Safety will be confirmed by evaluating the MR scan related ImageReady System complication-free rate (CFR) between the MR Scan and the MRI Visit + 1 Month.

For the purpose of this endpoint, a MR scan-related ImageReady System complication will be defined as those complications that are related to the MR scan and ImageReady System. All complications that the site reports as related to the MR scan and ImageReady System will be adjudicated by an external committee for relation to the MR scan. Complications that are determined to be associated with the MR scan will be considered MR scan-related complications and count against this endpoint. Complication is defined as serious adverse event or permanent loss of device functions (i.e. pacing or defibrillation).

The performance goal of the primary safety endpoint for the ENABLE MRI study (MR scan related ImageReady System complication free rate) was 90%. There is no hypothesis testing in the MR ICD study, and it can be considered reasonable if up to 2 failed cases of primary safety endpoint event may occur. Descriptive statistics will be conducted for the endpoint events.

The data set for the primary safety endpoint will include all subjects who undergo the study-required MR scan sequences (scan sequences initiated, whether complete or not). The time window for MRI + 1 Month visit is 30±7 days post MR scan, so it will capture events within at least 23 days post scan. In this small sample size study, missing data will be excluded.

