### **13.1.6. Primary Effectiveness Endpoint 5: Pre-MR scan vs. 1 Month Post-MR Scan LV Sensed Amplitude**

Subjects will be considered a success if the average sensed amplitude at the MRI + 1 Month Visit remains  $\geq 5.0$  mV and above 50% of the pre-MR scan value, otherwise, it is a primary effectiveness endpoint 5 event.

The performance goal of this endpoint for the ENABLE MRI study was 85%. There is no hypothesis testing in the MR ICD study, and it can be considered reasonable if up to 2 failed cases of primary effectiveness endpoint 5 occur.

The data set for the primary effectiveness endpoint 5 will only include subjects who undergo the study-required MR scan and complete all the sequences, and will not include subjects that meet any of the following exclusions:

- Has a medically necessary scan between implant and the MRI + 1 Month Visit
- Fails to meet labeled MRI Conditions of Use
- Experiences a lead-related complication between MRI Visit and the MRI + 1 Month Visit
- Average LV sensed amplitude <5mV pre-MR scan

The time window for MRI + 1 Month visit is  $30\pm 7$  days post MR scan, so it will capture events within at least 23 days post scan. In this small sample size study, missing data will be excluded.

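### The SAP drops the protocol's limit of 2 failures for effectiveness and puts in its place performance goals with no value, a lower-bound clause that almost any result meets, and Wald limits that are invalid at these sample sizes

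*Combined protocol and SAP*

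**What the plan says.** **Protocol.** The synopsis accepts "up to 2 failed cases of endpoint event occur in each of the five primary effectiveness endpoints", and sections 13.1.2 to 13.1.6 repeat the count endpoint by endpoint; for the LV pacing threshold, "it can be considered reasonable if up to 2 failed cases of primary effectiveness endpoint 4 occur", and for LV sensing, "it can be considered reasonable if up to 2 failed cases of primary effectiveness endpoint 5 occur". There is no hypothesis test. Beside the count the protocol cites goals from ENABLE MRI. For safety (13.1.1): "The performance goal of the primary safety endpoint for the ENABLE MRI study (MR scan related ImageReady System complication free rate) was 90"%. For the RV pacing threshold (13.1.3): "The performance goal of this endpoint for the ENABLE MRI study was 87"%. The LV pacing threshold (13.1.5) also has 87%, both sensing endpoints (13.1.4, 13.1.6) have 85%, and endpoint 1 has none. LV measurements need an LV lead. Section 12.5.1.3 says: "If the subject does not have an active implanted LV lead, then skip to the next section". Section 13.3 plans 10 ICD and 10 CRT-D subjects, with at least 8 of each completing the scan.

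**SAP.** Section 3.1 repeats the limit of 2 for safety. The matching sentence for effectiveness in 3.2 has no number, and the endpoint definitions that follow do not supply one. Section 3.4 says that there is no formal hypothesis, but lets an individual performance goal settle the status of each endpoint. Section 5.1.1 speaks of deriving performance goals, and expects endpoint success to exceed the lower confidence limit. Section 7.5 refers to hypotheses for the primary endpoints and asks for Wald limits in the output beside Clopper-Pearson. None of the goal values (90%, 87%, 85%) appears in the SAP.

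**The concern.** The failure count is the only acceptance criterion fixed in advance for effectiveness, and the Phase I data are meant to support registration. An analyst who works from the SAP alone finds three substitutes: a count without a number, a goal without a value, and a comparison with the lower limit that hardly any result can fail. Which one is used could decide how the same data are described. The Wald limits would then put impossible or zero-width intervals beside the exact ones.

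The count also means different things for different endpoints, because the LV endpoints have about half the subjects. Neither document says so. Sensing gives the cleanest comparison, because the success rule for RV ("above 50% of the pre-MR scan value, otherwise, it is a primary effectiveness endpoint 3 event") and for LV ("above 50% of the pre-MR scan value, otherwise, it is a primary effectiveness endpoint 5 event") is the same, with the same 5.0 mV floor and the same cited 85%. The pacing-threshold endpoints are not like for like: the allowed rise is 0.5 V for RV and 1.0 V for LV.

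**Working it through.** **Inputs.** Count of 2 (synopsis; 13.1.2–13.1.6). Group sizes from 13.3. ENABLE MRI goals from 13.1.1 and 13.1.3–13.1.6. Exact two-sided 95% limits as in SAP 5.1.1.

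**The plan's own figure.** 10 − 2 = 8 per group and 2 × 8 = 16 in total, which reproduces the stated minimum. The protocol gives no derivation for the count of 2.

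**1. What two failures mean.** Observed success is (n − 2)/n.

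| Endpoints | n | Success | Exact 95% limits | Cited goals |
|---|---|---|---|---|
| LV (4, 5) | 8 | 6/8 = 75.0% | 34.9–96.8% | 87%, 85% |
| LV (4, 5) | 10 | 8/10 = 80.0% | 44.4–97.5% | 87%, 85% |
| RV (2, 3) | 16 | 14/16 = 87.5% | 61.7–98.4% | 87%, 85% |
| RV (2, 3) | 20 | 18/20 = 90.0% | 68.3–98.8% | 87%, 85% |

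Two failures reach 85% from n = 14 (12/14 = 85.7%; 11/13 = 84.6%) and 87% from n = 16 (13/15 = 86.7%). The planned CRT-D group has 10. Nor is 75% a floor: the exclusions and missing data in 13.1.5 and 13.1.6 come on top of the minimum of 8. If, as an assumption, 7 were evaluable, 5/7 = 71.4%.

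**2. The lower-bound clause in SAP 5.1.1.** For x successes in n, the exact lower limit is the 2.5% quantile of a Beta(x, n − x + 1) distribution. It lies below x/n whenever x is at least 1 (checked for n = 1 to 40). Even 1/8 passes: the observed rate is 12.5% and the lower limit is 1 − 0.975^(1/8) = 0.3%. The clause therefore separates nothing but zero successes from the rest.

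**3. The missing goal value.** Suppose a reader fills the gap in SAP 3.4 with the ENABLE MRI goals and compares them with the exact lower limit. With no failures that limit is 0.025^(1/n): 63.1% (n = 8), 69.2% (n = 10), 79.4% (n = 16) and 83.2% (n = 20). All are below 85%, so even 20/20 would miss every cited goal. One result, 6/8 on endpoint 4, then reads as follows:

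| Reading | Outcome for 6/8 |
|---|---|
| Protocol count | within the limit |
| SAP 5.1.1 clause | met (75.0% > 34.9%) |
| Observed rate against 87% | below |
| Exact lower limit against 87% | below |

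**4. Wald limits in SAP 7.5.** p ± 1.96·√[p(1 − p)/n].
- No failures: the standard error is 0, so the limits are 100–100% at any n; the exact limits at 8/8 are 63.1–100%.
- 6/8: √(0.75 × 0.25/8) = 0.153, so 75.0 ± 30.0 = 45.0–105.0%.
- 18/20: √(0.9 × 0.1/20) = 0.067, so 90.0 ± 13.1 = 76.9–103.1%.

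**5. What two LV failures do not show.** The exact intervals for 6/8 and 8/10 both contain 85% and 87%. If true success were 87%, two or more failures would occur with probability 1 − 0.721 = 27.9% at n = 8 and 1 − 0.620 = 38.0% at n = 10.

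**The case against.** The study is descriptive. Both documents say that there is no hypothesis test, and the goals are attributed to ENABLE MRI, a study of 500 subjects. The count, the 10 CRT-D subjects and the minimum of 8 stand together in the synopsis, so 75–80% is one division away. The SAP says that it is based on protocol version AC, so its omission does not cancel the count. It already requires counts, percentages and Clopper-Pearson intervals (3.6, 5.1.1, 5.1.2), and the Wald request sits in a section offered as sample code.

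Most of this stands, and it limits the point. A reader might infer that the LV limit fails the 87% and 85% goals, or that two LV failures would be inconsistent with them. The documents do not support either inference. The goals are not adopted here, the documents do not say whether ENABLE MRI set them against an estimate or a confidence limit, and the exact intervals contain them. A reader might also infer that the LV count must be cut to 1. That would be a different trade-off and not the correction of an error.

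The SAP wording is not rescued by these arguments. A descriptive plan still needs its one yardstick stated, and 3.4 and 5.1.1 put other decision language in its place. Sample code or not, 7.5 says that the Wald limits have to be presented.

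**Conclusion.** The SAP is wrong as written on four counts: the effectiveness limit has no number (3.2), an unvalued goal is given the deciding role (3.4, 5.1.1), the lower-bound clause is met by any result with at least one success (5.1.1), and invalid Wald limits are required (7.5). These should be corrected. The difference between 75–80% (LV) and 87.5–90% (RV) at the same count is context that the report should make explicit; it is not a failed test. The percentages rest on the evaluable numbers of 13.3, 8–10 for LV and 16–20 for RV, before exclusions and missing data; with fewer subjects the LV figure falls further. The lower-limit reading in step 3 is a possible use of vague wording and is not a planned analysis.

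**What to change.** 1. **SAP 3.2.** Restore the count, for example: *For each of endpoints 1 to 5, no more than two failures is regarded as reasonable, counted among the evaluable subjects in that endpoint's data set in protocol 13.1.2 to 13.1.6, with success and failure as defined there.* Naming the data set matters because SAP 5.1.2 presents the endpoints for more than one population. Restore the protocol's success definitions at the same time: SAP endpoint 3 (RV sensing) carries the pacing-threshold rule, and endpoint 5 (LV sensing) has no rule.
2. **SAP 3.4 and 5.1.1.** Delete the performance-goal wording and the lower-bound clause, and refer to the protocol count. In 7.5, speak of primary endpoints and not of hypotheses.
3. **SAP 7.5.** Remove the Wald statement and the requirement to show its limits; present Clopper-Pearson only.
4. **Reporting.** Give each result as failures/n with exact limits. If an LV endpoint has two failures at n = 8–10, state that the observed rate (75–80%) is below the cited ENABLE MRI goal, that the exact interval includes the goal, and that meeting the count does not show that the goal is met.

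The cost is SAP wording: no extra subjects and no change to the protocol's count. SAP 5.4 provides for an amended SAP approved before the analyses. If they have already been run, record the changes and the reason in the clinical study report.

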### **13.1.6. Primary Effectiveness Endpoint 5: Pre-MR scan vs. 1 Month Post-MR Scan LV Sensed Amplitude**

Subjects will be considered a success if the average sensed amplitude at the MRI + 1 Month Visit remains  $\geq 5.0$  mV and above 50% of the pre-MR scan value, otherwise, it is a primary effectiveness endpoint 5 event.

The performance goal of this endpoint for the ENABLE MRI study was 85%. There is no hypothesis testing in the MR ICD study, and it can be considered reasonable if up to 2 failed cases of primary effectiveness endpoint 5 occur.

The data set for the primary effectiveness endpoint 5 will only include subjects who undergo the study-required MR scan and complete all the sequences, and will not include subjects that meet any of the following exclusions:

- Has a medically necessary scan between implant and the MRI + 1 Month Visit
- Fails to meet labeled MRI Conditions of Use
- Experiences a lead-related complication between MRI Visit and the MRI + 1 Month Visit
- Average LV sensed amplitude <5mV pre-MR scan

The time window for MRI + 1 Month visit is  $30\pm 7$  days post MR scan, so it will capture events within at least 23 days post scan. In this small sample size study, missing data will be excluded.

### **13.2. Ancillary Assessments**

The ancillary endpoints are not formal endpoints.

#### **13.2.1. Assessment of RV and LV Impedances**

The changes in RV and LV impedances pre-MR scan versus 1 Month post-MR scan (MRI Visit and MRI + 1 Month Visit) will be presented in the study report.

#### **13.2.2. Assessment of RA lead measurements**

The changes in RA lead measurements including pacing thresholds, sensed amplitudes and impedances, between pre- and 1 Month post-MR scan measurements will be presented in the study report.

#### **13.2.3. Assessment of VT/VF post MR scan**

The detection time (first elapsed time), therapy given and conversion result, shocking impedance (if applicable) for post MR scan VT/VF episodes will be presented in the study report.

#### **13.2.4. Assessment of Programming the MRI Protection Mode**

The following information will be summarized for both study-related MR scans and medically necessary MR scans:

- Duration of the PG in the MRI Protection Mode
- Time from the start of the MRI Protection Mode to the start of the MR scan
- Time from the end of the MR scan to exiting the MRI Protection Mode

### **13.2.5. Assessment of Image Artifacts for non-medically necessary MR scans**

MR image quality scores will be presented in the study report.

### **13.3. Sample Size**

The MR ICD study is a small sample size study without any formal hypothesis testing. Twenty subjects (10 with ICD and 10 with CRT-D) will be enrolled. It is assumed that the attrition should not be more than 2 cases in each group, so that at least 8 ICD subjects (at least 1 single chamber and 1 dual chamber ICD) and 8 CRT-D subjects shall undergo required MR scan and complete all the sequences. Sample size might be expanded to meet this assumption.

### **13.4. General Statistical Methods**

#### **13.4.1. Control Bias**

Selection of patients will be made from the Investigator's usual patient load. All patients meeting the eligibility criteria and having signed the ICF will be eligible for enrollment in the study. An independent Clinical Events Committee (CEC) will determine the MR Scan-related ImageReady System complications. The study will be conducted in approximately 5 sites and one single site may not enroll more than 10 subjects generally.

#### **13.4.2. Data Analyses**

The MR ICD study is a multi-center, prospective, single –arm study. There is no formal hypothesis testing. Descriptive statistics will be conducted for the endpoint events. Please refer to section [13.1](#) for endpoint assessment.

#### **13.4.3. Data Set, Subgroups and Missing Data**

The data set for the safety endpoint will include all subjects who undergo the study-required MR scan sequences (scan sequences initiated, whether complete or not). The data set for the effectiveness endpoint will only include subjects who undergo the study-required MR scan and complete all the sequences, and will not include subjects that meet any of the following exclusions:

- Has a medically necessary scan between implant and the MRI + 1 Month Visit
- Fails to meet labeled MRI Conditions of Use

- Experiences a lead-related complication between MRI Visit and the MRI + 1 Month Visit MRI

Subjects whose average RV sensed amplitude <5mV pre-MR scan will also be excluded for primary effectiveness endpoint 3 assessment, and subjects whose average LV sensed amplitude <5mV pre-MR scan will also be excluded for primary effectiveness endpoint 5 assessment.

There is no formal subgroup analysis in the MR ICD study, however, descriptions may be grouped on study site, subject sex, device type (single chamber ICD, dual chamber ICD and CRT-D), etc.

The primary endpoints for the MR ICD study are comparisons between MRI Visit and the MRI + 1 Month Visit, absence of either comparator will be missing data for that endpoint. Missing data will be excluded for endpoint assessment in this small sample size MR ICD study.

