#### **ii. Primary Effectiveness Endpoint 2: Pre-MR Scan vs. 1 Month Post-MR Scan RV Pacing Threshold at 0.5 ms:**

*The data set for the primary effectiveness endpoint 2 will only include subjects who undergo the study-required MR scan and complete all the sequences, and will not include subjects that meet any of the following exclusions:*

- *Has a medically necessary scan between implant and the MRI + 1 Month Visit*
- *Fails to meet labeled MRI Conditions of Use*
- *Experiences a lead-related complication between MRI Visit and the MRI + 1 Month Visit*

The primary effectiveness endpoint 2 is defined as ‘an increase in average pacing thresholds  $\leq 0.5V$  (at 0.5 ms) from pre-MR Scan to MRI Visit + 1

Month follow-up will be considered as success', otherwise it's a failure (event).

iii. **Primary Effectiveness Endpoint 3: Pre-MR scan vs. 1 Month Post-MR Scan RV Sensed Amplitude:**

*The data set for the primary effectiveness endpoint 3 will only include subjects who undergo the study-required MR scan and complete all the sequences, and will not include subjects that meet any of the following exclusions:*

- *Has a medically necessary scan between implant and the MRI + 1 Month Visit*
- *Fails to meet labeled MRI Conditions of Use*
- *Experiences a lead-related complication between MRI Visit and the MRI + 1 Month Visit*
- *Average RV sensed amplitude <5mV pre-MR scan*

The primary effectiveness endpoint 3 is defined as 'an increase in average pacing thresholds  $\leq 0.5V$  (at 0.5 ms) from pre-MR Scan to MRI Visit + 1 Month follow-up will be considered as success', otherwise it's a failure (event).

iv. **Primary Effectiveness Endpoint 4: Pre-MR Scan- vs. 1 Month Post-MR Scan LV Pacing Threshold at 0.5 ms:**

*The data set for the primary effectiveness endpoint 4 will only include subjects who undergo the study-required MR scan and complete all the sequences, and will not include subjects that meet any of the following exclusions:*

- *Has a medically necessary scan between implant and the MRI + 1 Month Visit*
- *Fails to meet labeled MRI Conditions of Use*
- *Experiences a lead-related complication between MRI Visit and the MRI + 1 Month Visit*

The primary effectiveness endpoint 4 is defined as 'increase in average pacing thresholds  $\leq 1.0V$  (at 0.5 ms) from pre-MR Scan to MRI Visit + 1 Month follow-up will be considered a success', otherwise it's a failure (event).

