### **5.3.3 Procedure Characteristics and performance**

Procedure evaluation summary for Atrial Fibrillation., RA, RV & LV lead measurements and PNS threshold with New Episode of polymorphic and Image Artifacts measurement are summarized. Device Information like Pulse generator, Defibrillation Lead & LV Lead are summarized for Implant populations at Implant procedure, Pre-Discharge, MNS Pre - Post MR Scan visits, Pre MR-Scan Visit, Post MR Scan Visit & MRI Visit+1 Month procedure, MRI Visit+ 3-month, MRI Visit+ 6-month, MRI

Visit+ 9-month visits and Implant+1-year visits. However, the results will be summarized only for the above available timepoint visits.

A comprehensive listing based on MRI information by visits is presented by subject with MRI protection mode, Time of MR scan initiation and completion, exiting MRI protection and radiologist scores are presented.

- A listing based on pacing threshold LEAD (RA/RV/LV) for each subject with site
- A listing based on Sensed Amplitude LEAD (RA/RV/LV) for each subject with site
- A listing based on Pacing Impedance LEAD (RA/RV/LV) for each subject with site
- A listing based on Shocking Impedance LEAD (RA/RV/LV) for each subject with site

will be presented based on available analysis time points including Implant procedure, Pre-Discharge, MNS Pre - Post MR Scan visits, Pre MR-Scan Visit, Post MR Scan Visit & MRI Visit+1 Month procedure, MRI Visit+ 3-month, MRI Visit+ 6-month, MRI Visit+ 9-month visits and Implant+1-year visits. All the above listings are based on Implant populations.

A summary table for all medications with Generic medication name summarized for cardiovascular medication usage based on Implant population presented for Implant, pre-Discharge, MR Scan, MRI Visit+1-week, MRI Visit+1-month, MRI Visit+ 3-month, MRI Visit+ 6-month , MRI Visit+ 9-month visits and Implant+1-year visits.

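### Subjects starting below 5 mV are left out of sensing endpoints 3 and 5 entirely, although the 50% condition can be judged for them; a separate row should report it

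*Combined protocol and SAP*

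**What the plan says.** **Success rule (protocol only).** For endpoint 3, protocol 13.1.4 requires the 1-month RV average to stay at or over 5.0 mV "and above 50% of the pre-MR scan value, otherwise, it is a primary effectiveness endpoint 3 event". For endpoint 5, protocol 13.1.6 asks the same of the LV average: at least 5.0 "mV and above 50% of the pre-MR scan value, otherwise, it is a primary effectiveness endpoint 5 event". Both parts must be met.

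**Exclusion.** Protocol 13.4.3 says "Subjects whose average RV sensed amplitude <5mV pre-MR scan will also be excluded for primary effectiveness endpoint 3 assessment" and, for the LV lead, "subjects whose average LV sensed amplitude <5mV pre-MR scan will also be excluded for primary effectiveness endpoint 5 assessment". The bullets in protocol 13.1.4 and 13.1.6 and in SAP 3.2 (iii and v) repeat this, for example "Average RV sensed amplitude <5mV pre-MR scan" and "Average LV sensed amplitude <5mV pre-MR scan"; SAP 4.1 carries it under the Implant population. No section offers a different way of scoring these subjects.

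**Decision reading.** There is no hypothesis test. Each effectiveness endpoint is regarded as reasonable with up to 2 failures, whatever the denominator.

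**Where the values otherwise appear.** SAP 5.3.3 plans by-visit summaries and "A listing based on Sensed Amplitude LEAD (RA/RV/LV) for each subject with site". SAP 5.1.3 plans mean plots of sensed amplitude.

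**SAP text that does not fit.** SAP 3.2 (iii) gives endpoint 3 the pacing-threshold criterion (an increase of at most 0.5 V). SAP 3.2 (v) gives endpoint 5 no success criterion. SAP 5.1.1 bases all five effectiveness endpoints on the Implant population, whereas the last paragraph of SAP 5.1.2 promises them for the Intent population too. The Intent definition in SAP 4.1 has no 5 mV exclusion.

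**The concern.** The two parts of the success rule answer different questions. The 5.0 mV part asks whether an adequate signal stayed adequate, which cannot be asked of a lead already below 5 mV. The 50% part asks whether the signal fell substantially after the scan. That is the change for which protocol 8.2 names endpoints 3 and 5, and it can be computed from any baseline. The exclusion removes both parts.

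The subjects concerned can be enrolled, because the eligibility criteria in protocol 10.2 and 10.3 set no minimum amplitude. They are scanned, and every implanted lead is measured in three sets before the scan and three at 1 month (protocol 12.7.1, 12.8.1). The paired averages will exist. At stake is whether the trial makes any pass-or-fail judgement on a large loss of sensing in the subjects with the least sensing margin.

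**Working it through.** **Inputs.** Let b be the pre-scan average and m the 1-month average. Success: m ≥ 5.0 mV and m > 0.5b (protocol 13.1.4, 13.1.6). Excluded: b < 5 mV. Planned: 10 ICD and 10 CRT-D subjects, with at most 2 lost per group (protocol 13.3). Allowance: 2 failures per endpoint. Reference goal in the parent study for both endpoints: 85%. The number excluded (k) and the number of those who lose at least half their amplitude (c) are not in the documents and are varied below.

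**1. The plan's own figure.** 10 − 2 = 8 per group, so 16 of 20 complete the scan at minimum. Endpoint 3 therefore rests on at most 16–20 subjects and endpoint 5, which needs an LV lead, on at most 8–10 CRT-D subjects. These figures reproduce.

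**2. Which part can be judged at which baseline.** 0.5b reaches 5.0 mV at b = 10 mV. From 5 to 10 mV the 5.0 mV part governs; from 10 mV upward the 50% part governs. Below 5 mV the 50% limit is still defined:

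| b (mV) | limit 0.5b (mV) |
|---|---|
| 4.8 | 2.4 |
| 4.0 | 2.0 |
| 3.0 | 1.5 |

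A fall from 4.8 to 1.0 mV is (4.8 − 1.0)/4.8 = 79%, well past the 2.4 mV limit, and is not an event as planned.

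**3. Effect on the reading.** If f subjects fail among those with b ≥ 5 mV, the plan reads f against 2. Adding the unjudged falls changes the picture only when f ≤ 2 but f + c > 2. With c = 1 that requires f = 2 exactly; with c = 0 nothing changes. Taking f = 2, k = 2 and c = 1:

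| Endpoint | Paired subjects | Main count as planned | Excluded subjects failing the 50% part | Subjects failing in all |
|---|---|---|---|---|
| 3 | 20 | 2 of 18 (88.9% success) | 1 of 2 | 3 |
| 3 | 16 | 2 of 14 (85.7%) | 1 of 2 | 3 |
| 5 | 10 | 2 of 8 (75.0%) | 1 of 2 | 3 |
| 5 | 8 | 2 of 6 (66.7%) | 1 of 2 | 3 |

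**4. Effect on the denominator.** The allowance stays at 2 while the denominator shrinks. P(at most 2 failures) at a true failure rate of 15% (1 − 85%) is binomial. For endpoint 5 it rises from 0.895 (n = 8) to 0.953 (n = 6); for endpoint 3, from 0.405 (n = 20) to 0.480 (n = 18). With no failures, the exact 95% lower limit is 0.025^(1/n): 63.1% at n = 8 and 54.1% at n = 6. Expansion of enrolment (protocol 11.4, 13.3) is tied to completing the sequences and to device and lead types, not to being evaluable for these endpoints, so excluded subjects are not replaced.

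**5. Other routes to a judgement.**
- The ancillary assessments in protocol 13.2.1 and 13.2.2 cover RV and LV impedances and RA measurements, not change in RV or LV sensing.
- The safety endpoint needs an SAE or a permanent loss of function. The functions named are pacing and defibrillation (protocol 13.1.1), and the site must first report the event as related.
- In a mean plot, a 3.8 mV fall in one of 20 subjects moves the mean by 3.8/20 = 0.19 mV.
- The Intent summary in SAP 5.1.2, if scored with the protocol rule, would fail any subject who stayed below 5 mV, including one unchanged at 4.8 mV. It would not isolate a true fall.

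**The case against.** The exclusion is deliberate and stated consistently in both documents. Amplitude cannot remain at 5.0 mV or more in a subject who starts lower. The protocol takes its design and reference goal from the parent study, so changing the main definition would weaken that comparison. This stands: it justifies the present main count and the waiver of the 5.0 mV part. It gives no reason against reporting the 50% part.

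The event may also be rare. Protocol section 4 cites a registry of non-thoracic scans in which R-wave falls of at least 50% in ICD subjects were 0.2% immediately after the scan and 0 in the long term. At 0.2%, the chance of at least one among k = 1 to 3 excluded subjects is 1 − 0.998^k, about 0.2% to 0.6%. This is the only rate in the documents and it suggests a small practical effect. However, it gives no figure for low baselines, and this trial centres its RF-intensive sequences on the thoracic spine.

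A third objection concerns pooling. If subjects judged on one part joined those judged on two, a fall from 4.8 to 2.5 mV (48%) would enter the same rate as a success. That objection is sound, and it is why the added row must stay separate.

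A reader might infer that such a fall would never be seen. The documents do not support that. It would be visible in the per-subject listing, it could be reported as an adverse event or device deficiency, and an MR-related SAE could count for safety. A reader might also take the abrupt 5.0 mV boundary for subjects just above it as part of this point. Those subjects are included and scored, so that is a different question about the cut-off.

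**Conclusion.** The point holds in a limited form. In the main (Implant) analysis, a subject starting below 5 mV cannot count as an event on endpoint 3 or 5, however large the fall, although the data to judge the 50% part are collected.

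The size is unknown, because the documents give no frequency of baselines below 5 mV; every k and c above is an assumption. A single unjudged fall matters to the allowance of two only if exactly two other subjects fail. With none, the reading is unchanged. The documents therefore do not support saying that the exclusion biases the result or reverses a conclusion. The loss of precision is real but decides nothing, since no test is made.

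Nor is it settled that these subjects go unscored everywhere: SAP 5.1.2 can be read as including them through the Intent population, while SAP 3.2 and 5.1.1 point the other way. The two-part rule is itself only in the protocol, so the SAP section that would carry the correction is already incomplete.

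**What to change.** Amend the SAP before the analyses are run:

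- **Main row, unchanged.** Keep the two-part count in subjects with a pre-scan average of at least 5 mV, as the row comparable with the parent study.
- **One added row for each of endpoints 3 and 5.** Judge the 50% part in every subject with paired averages. State how many were excluded for a baseline below 5 mV and how many of those fail the 50% part. Pre-specify that this row is considered alongside the two-failure reading, and do not merge the two success definitions into one rate.
- **SAP 3.2.** Replace the pacing-threshold text under endpoint 3 with the protocol's two-part criterion, and give endpoint 5 its criterion.
- **SAP 5.1.2.** Reconcile the Intent-population summary with SAP 3.2 and 5.1.1, saying whether the 5 mV exclusion applies there.

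The cost is one table row per endpoint and some SAP wording, with no new data. The downside is that the reported picture may be slightly less favourable. The added row does not restore the denominator of the main row, so the number excluded should be shown beside it.
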